3DCRT	3-Dimensional Conformal Radiation Therapy	3D conformal radiation therapy
ADL	Activities of Daily Living	Daily activities
AE	Adverse Events	Bad Incident
WHITE	Serum Albumin	Serum albumin
OLD	Alanine Aminotransferase	Alanine aminotransferase
APTT	Activated Partial Thromboplastin Time	Activation of partial thromboplastin time
AST	Aspartate Aminotransferase	Glutamate aminotransferase
GOOD	Blood Urea Nitrogen	Urea nitrogen
Ccr	Endogenous Creatinine Clearance Rate	Creatinine clearance
CFDA	China Food and Drug Administration	State Food and Drug Administration
CH	Chordoma	Chordoma
CK-MB	Creatine Kinase Isoenzymes-MB	Creatine kinase isoenzymes
CP	Child-Pugh	-
CR	Complete Response	Complete remission
CRA	Clinical Research Associate	Clinical monitor
CRF	Case Report Form	Case report form
CTCAE	Common Terminology Criteria for Adverse Events	Common terminology criteria for adverse events
cTn	Cardiac Troponin	Troponin
CTV	Clinical Target Volume	Clinical targets
DART	Dynamic Adaptive Radiation Therapy	Dynamically adapted radiotherapy techniques
DIPS	Digital Imaging Positioning System	Digital image positioning system
DOR	Duration of Response	Duration of mitigation
DRR	Digitally Reconstruction Radiograph	Digitally reconstructed radiography
DVH	Dose Volume Histogram	Volume dose histogram
EC	Ethics Committee	Ethics Committee
ECOG	Eastern Cooperative Oncology Group	Eastern U.S. Oncology Collaborative Group
eCRF	Electronic Case Report Form	Electronic case report form

Abbreviations	Full spelling in English	Chinese translation
EDC	Electronic Data Capture System	Electronic data collection systems
ERA	Erythrocyte	Urine red blood cell count
FAS	Full Analysis Set	Full analysis set
FPG	Fasting Plasma Glucose	Fasting blood sugar
GCP	Good Clinical Practice	Good Clinical Trial Management Practice for Medical Devices
GLU	Glucose	Urine sugar
GTV	Gross Tumor Volume	Gross tumor area
HBV	Hepatitis Virus B	Hepatitis B virus
HCG	Human Chorionic Gonadotropin	Blood pregnancy test
HCV	Hepatitis Virus C	Hepatitis C virus
HGB	Hemoglobin	haemoglobin
HIV	Human Immunodeficiency Virus	Human immunodeficiency virus
ICF	Informed Consent Form	Informed consent
IGRT	Image-Guided Radiation Therapy	Image-guided radiation therapy
IMPT	Intensity Modulated Proton Therapy	Conformal intensity-modulated proton therapy
IMRT	Intensity Modulated Radiation Therapy	Conformal intensity-modulated radiation therapy
INR	International Normalized Ratio	International standardized ratio
LET	Linear Energy Transfer	Linear energy transfer
LEU	Leucocyte	Urine white blood cell count
LGG	Low-Grade Glioma	Low-grade glioma
LVEF	Left Ventricular Ejection Fractions	Left ventricular ejection fraction
Mb	Myoglobin	myoglobin
NEUT	Neutrophil	Neutrophils
NMPA	National Medical Products Administration	State Drug Administration
NPC	Nasopharyngeal Carcinoma	Nasopharyngeal carcinoma
NSCLC	Non-Small-Cell Lung Cancer	Non-small cell lung cancer
NYHA	New York Heart Association	New York Heart Society
OAR	Organ at Risk	Endangers organs

Abbreviations	Full spelling in English	Chinese translation
WHETHER	Occult Blood Test	Occult blood test
OIS	Oncology Information System	Radiation therapy management software
OPC	Oropharyngeal Cancer	Oropharyngeal cancer
ORR	Objective Response Rate	Objective response rate
THE	Overall Survival	Overall lifetime
PBS	Pencil Beam Scanning	Pen beam scanning
PD	Progressive Disease	Disease progression
PFS	Progression-free Survival	Progression-free survival
PLT	Platelet	platelet
PPS	Per-Protocol Set	Conforms to the scenario set
PR	Partial Response	Partial remission
FOR	Protein	Urine protein
PRV	Planning Organ-at-Risk Volume	Plan to endanger organs
PSA	Prostate Specific Antigen	Prostate-specific antigen
PSI	Paul Scherrer Institute	Paul Scheller Institute, Switzerland
PT	Prothrombin Time	Prothrombin time
PTC	Proton Treatment Console	Proton therapy console
PTV	Planning Target Volume	Plan the target
QA	Quality Assurance	quality assurance
QOL	Quality-of-Life	Quality of life assessment
RBC	Red Blood Cell	erythrocyte
RBE	Relative Biological Effectiveness	Relative biological effects
RECIST 1.1	Response Evaluation Criteria in Solid Tumors RECIST Version 1.1	Tumor efficacy evaluation criteria version 1.1
RVR	Remaining Volume at Risk	Remaining danger areas
SAE	Serious Adverse Events	Serious adverse events
SBRT	Stereotactic Body Radiation Therapy	Stereotactic radiosurgery
SCIC	Second Channel Integrity Check	Second integrity check
SCLC	Small Cell Lung Cancer	Small cell lung cancer

Abbreviations	Full spelling in English	Chinese translation
Scr	Serum Creatinine	creatinine
SD	Stable Disease	The disease is stable
SDV	Source Data Validation	Raw data verification
SLD	Sum of Longest Diameter	The sum of the longest diameters of the tumor
SOBP	Spread-out Bragg Peak	Extend Bragg Peak
SOP	Standard Operating Procedure	Standard operating procedures
SS	Safety Set	Security datasets
ETC	Serum Total Bilirubin	Total serum bilirubin
TV	Treated Volume	Treatment area
ULN	Upper Limit of Normal	Upper limit of normal value
VMAT	Volumetric-Modulated Arc Therapy	Volumetric rotational intensity-modulated radiotherapy
WBC	White Blood Cell	white blood cell
WHO	World Health Organization	World Health Organization

Protocol summary

The name of the experiment	Varian ProBeam360 Proton Therapy System China Clinical Trial (Wuhan).
Device name	proton therapy system (hereinafter referred to as ProBeam360).
Manage categories	Class III (classification: 05 radiotherapy equipment--01 radiotherapy equipment--02 medical light ion therapy system).
Scope of application	Proton therapy system provide precision radiation therapy protons for lesions, tumors, and conditions in the patient's body that require radiation therapy.
Scope of the test	Cancer patients, including tumors of intracranial, head and neck, chest, abdomen, spine, pelvis, limbs, etc
Trial design	Prospective, open-label, single-centered, single-group target value method
Trial and long-term follow-up purposes	
Clinical trial (screening-short-term follow-up): The data obtained by using Proton Beam system (ProBeam360) for radiation therapy in tumor patients compared with the target value to evaluate the effectiveness and safety of ProBeam360 for radiation therapy in tumor patients to provide clinical basis for product registration application.
 
Long-term follow-up: The long-term efficacy and safety of ProBeam360 for radiation therapy in cancer patients were evaluated by using the long-term follow-up data of ProBeam360 for radiation therapy in cancer patients.

Sample size	
At least 47 participants are enrolled in this trial.
 
Assuming the expected primary efficacy evaluation indicator (3-month tumor local control rate) is 95%, the target value is 80%, the bilateral significance level is 0.05, and the confidence level is 80%, data from 42 participants are required at the end of the 3-month observation period.
 
Considering the expected dropout rate of 10% during short-term follow-up of clinical trials, 47 subjects are required to be enrolled.
 
(1) The number of cases of tumors in the intracranial, head and neck, chest, abdomen, spine, pelvic cavity, and limbs should be evenly distributed as much as possible.
 
(2) The Intensity Modulated Proton Therapy (IMPT) technology and exercise management system should be used and validated in this study.

clinical trial	
Number of institutions	1 site
The expected duration of the participant's participation	The screening period from signing the informed consent form to enrollment is expected to be 4 weeks, the treatment period is 1~8 weeks, and the follow-up after the last treatment are divided into short-term follow-up and long-term follow-up, and the maximum duration of expected participation of each subject from screening to the end of short-term follow-up is 12 weeks +3 months. Long-term follow-up continued after the end of the short-term follow-up until the fifth year after the end of the last radiotherapy. (After a 3-month follow-up after the last treatment, a "Medical Device Clinical Trial Report" will be issued for the registration of this trial

product Declaration.)

Expected overall duration of clinical trials and long-term follow-up	
The first subject is expected to be enrolled in June 2024, and the clinical trial institution expects to enroll 12 subjects per month, for a total enrollment time of about 4 months, and the last subject ends the trial (short-term follow-up) is In April 2025.
 
The last subject to end long-term follow-up in January 2030.

Primary effectiveness	
Disease Control Rate (DCR).
 
Evaluation time: 3 months \pm 7 days after the last treatment.
 
Definition of indicators: Complete Response (CR), Partial Response (PR), Stable Disease (SD) for disease control. Proportion of participants who developed disease control three months after the end of the last radiotherapy.

Evaluation indicators	
Evaluation methodology: Response Evaluation Criteria in Solid Tumors RECIST Version 1.1 (RECIST 1.1) by an independent imaging review team in tumour CT or MRI imaging before and after treatment were assessed.
 
Participants who discontinued the trial for any reason (except loss to follow-up) before the end of radiation therapy were considered to have not controlled.

The main safety evaluation index	
(1) Common Terminology Criteria for Adverse Events (CTCAE) Grade 3 toxicity ratio
 
Evaluation time: 3 months \pm 7 days after the end of the last treatment.
 
Indicator definition: Proportion of subjects with grade 3 toxicity during the trial cycle.
 
Evaluation methodology: Investigators recorded AEs that occurred during the clinical trial cycle and graded them according to CTCAE V5.0.
 
(2) CTCAE grade 4 and 5 toxicity ratio
 
Evaluation time: the entire clinical trial cycle.
 
Indicator definition: Proportion of subjects with toxicity of grade 4 and 5 during the trial cycle.
 
Evaluation methodology: Investigators recorded AEs that occurred during the clinical trial cycle and graded them according to CTCAE V5.0.

Secondary effectiveness Evaluation indicators	
(1) Objective Response Rate (ORR) (three days, 1 month \pm 7 days, 2 months, \pm 7 days, 3 months, \pm 7 days after the end of the last treatment).
 
(2) DCR (three days, 1 month \pm 7 days, 2 months \pm 7 days) after the end of the last treatment
 
(3) Tumor markers (if required) (three days, 1 month \pm 7 days, 2 months \pm 7 days, 3 months \pm 7 days after the end of the last treatment).
 
(4) Tumor-specific symptoms (screening period, 1 month \pm 7 days, 2 months \pm 7 days, 3 months \pm 7 days).
 
(5) Product usability evaluation (ProBeam360 system, radiotherapy management software (Aria), radiotherapy planning software (Eclipse)) (the day of completion of the last treatment).

Secondary	
(1) CTCAE grade 1 and 2 toxicity ratio (3 months \pm 7 days after the end of the last

safety	treatment).
Evaluation indicators	
(2) Laboratory tests [3 days after the end of the last treatment, 1 Months \pm7 days, 2 months \pm7 days, 3 months \pm7 days].(3) Eastern Cooperative Oncology Group (ECOG) physical status grading [3 days after the end of the last treatment, 1 month\pm 7 days, 2 months\pm7 days, 3 months\pm7 days].(4) Incidence of adverse events (AEs) (3 months \pm 7 days after the end of the last treatment).(5) The incidence of Serious Adverse Events (SAEs) (3 months \pm 7 days after the end of the last treatment).(6) Incidence of device defects (after last treatment)
Eligibility criteria	
Inclusion Criteria (Major Criteria):
 
(1) $18 \leq \text{age} \leq 80$ years, Gender is not limited;(2) Patients diagnosed clinically as benign or malignant intracranial tumors, as well as malignant solid tumors in the head and neck, chest, abdomen, spine, pelvic cavity, and limbs, based on cellular or histopathological diagnosis and/or evidence from imaging, laboratory tests, etc. (recurrent patients may only have evidence from imaging, laboratory tests, etc.);(3) The target lesion is a measurable solid tumor, and the longest diameter of the lesion should be ≥ 10mm;(5) According to the researchers' assessment, the expected survival time exceeds 6 months;(6) ECOG physical condition is graded as 0 to 2;(7) Women of childbearing had negative results in the blood pregnancy test (Human Chorionic Gonadotropin, HCG) 7 days prior to the first treatment;(8) The subject or subject's guardian is able to understand the purpose of the study, demonstrate sufficient compliance with the protocol and sign informed consent form.
Specifications for the use of investigational medical device	
Exclusion Criteria (Major Criteria):
 
(1) The subject with radiotherapy contraindications, including the known genetic tendencies that increase the sensitivity of normal tissue radiotherapy or the accompanying diseases that lead to hypersensitivity to radiotherapy;(2) The subject with other uncontrolled tumors except that to be treated according to medical history or the investigator's estimation, or with other malignant tumors within five years prior to enrollment;(3) Implanted pacemakers or other metal prosthesis within the scope of proton therapy;(4) Other situations that investigator determines not suitable for enrollment.

Statistical analysis with SAS 9.4 software.

All data are described statistically, including baseline data, all efficacy measures, and all safety data. The measurement data give the mean, standard deviation, minimum, maximum, median, 25th quantile and 75th quantile; The counting data gives the frequency and composition ratio.

Effectiveness analysis

DCR was calculated and the Clopper-Pearson method was used to calculate the 95% confidence interval for tumor disease control. ORR was calculated and the Clopper-Pearson method was used to calculate the objective response rate 95% confidence interval. Descriptive statistics on the percentage change from baseline of the measurable sum of the longest diameter (SLD). The Waterfall Chart was made by the maximum percentage reduction in SLD per participant compared to the screening period.

The *Kaplan-Meier* method was used to calculate the median duration of response, median progression-free survival, median survival, and overall survival, and plotted *K-M* curves (long-term follow-up data).

Safety analysis

[figure not shown]
Descriptive statistics were used to classify organ systems in MedDRA medical terms, and the incidence, occurrence, and severity of adverse events, adverse reactions, and serious adverse events were summarized.

Laboratory indicators, ECOG physical status grading and other safety-related indicators were compared and evaluated before and after treatment, and clinical evaluation [no clinical significance, clinically significant (tends to normal), clinically significant (tends to be abnormal), not checked], CTCAE grade evaluation before and after treatment cross-tab.

The central effect is considered in the analysis process, and the general linear model is used for the measurement data and CMH for the counting data.

The baseline data analysis was performed using the Full Analysis Set (FAS); Effectiveness analysis uses FAS and Per Protocol Set (PPS); Security analysis uses the Safety Set (SS).

Trial flowchart

The body of the protocol

1 Sponsor information

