Evaluation method: The changes in tumor CT or MRI imaging before and after treatment were evaluated by an independent imaging review panel according to RECIST 1.1. At 3 months of radiographic evaluation, if PD is found, PET-CT is required to confirm it.

Calculation formula: DCR = number of disease control subjects / total number of subjects \times 100%.

Criteria: See RECIST 1.1 for details. At the time of 3-month imaging evaluation, if the patient is found to have PD, PET-CT examination is required to confirm it, if progress is confirmed, it is recorded as PD, if progress cannot be confirmed, it may

be false progression, and it is recorded as SD. If prostate cancer does not have biochemical recurrence, PET-CT examination is not required, and there is no metastasis by default, which is regarded as tumor control, and if biochemical recurrence occurs, it is regarded as tumor not controlled, and PET-CT is required to confirm tumor metastasis.

Note: Participants who aborted the trial for any reason (except loss to follow-up) before the end of the last radiation therapy were considered to have disease progression (PD) or were not controlled. Disease site evaluation uses the same approach as baseline, including consistent contrasted/non-contrast scans and prompt scanning. If changes are needed, the case must be discussed with a radiologist to determine whether an alternative approach is possible. If not, the objective situation in the future is unclear.

3.1.4.2 Secondary effectiveness evaluation indicators and their methods and timing of evaluation, recording, analysis

(1) Objective response rate (ORR).

Reason for selection: The Guidelines for the Review of Clinical Evaluation Technologies of Proton Carbon Ion Therapy Systems (CFDA Circular No. 4 [2018]) recommends the use of the latest version of the commonly used evaluation criteria for radiation oncology as the clinical trial evaluation criteria, so RECIST 1.1 is used. Relevant indicators as effectiveness evaluation criteria; Due to the particularity of the disease, the evaluation method recommended in the relevant diagnosis and treatment guidelines is selected. All of them can directly measure the effect of radiotherapy and are widely recognized and applied by clinicians.

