Definition of indicators: CR or PR after the end of treatment is considered objective remission, prostate cancer has no biochemical recurrence at the end of the last treatment, and no regional lymph nodes or distant metastasis are considered objective remission. Proportion of participants who experienced objective remission at each time point after the end of the last treatment.

Metric type: Qualitative.

Data collection time: screen period, 3 days, 1 month \pm 7 days, 2 months, \pm 7 days, 3 months, \pm 7 days after the end of the last treatment.

Evaluation time: 3 days, 1 month \pm 7 days, 2 months, \pm 7 days, 3 months, \pm 7 days after the last treatment.

Site of evaluation: Tumor receiving radiation therapy.

Evaluation method: The changes in tumor CT or MRI imaging before and after treatment were evaluated by an independent imaging review panel according to RECIST 1.1. At 3 months of radiographic evaluation, if PD is found, PET-CT is required to confirm it.

Calculation formula: ORR = number of subjects in objective response / total number of subjects \times 100%.

Criteria: See RECIST 1.1 for details. At the time of 3-month imaging evaluation, if the patient is found to have PD, PET-CT examination is required to confirm it, if progress is confirmed, it is recorded as PD, if progress cannot be confirmed, it may be false progression, and it is recorded as SD. If prostate cancer does not have biochemical recurrence, PET-CT examination is not required, and there is no metastasis by default, which is regarded as objective remission, and if biochemical recurrence occurs, it is regarded as not objectively remission, and PET-CT is required to confirm tumor metastasis.

Note: Participants who aborted the trial for any reason (other than loss to follow-up) before the end of the last radiotherapy were considered to have not responded objectively. Disease site evaluation uses the same approach as baseline, including consistent contrasted/non-contrast scans and prompt scanning. If changes are needed, the case must be discussed with a radiologist to determine whether an alternative approach is possible. If not, the objective situation in the future is unclear.

(2) Tumor disease control rate (DCR).

Reason for selection: DCR 3 months after the end of the last treatment was the primary evaluation index, and DCR at other follow-up time was used as a secondary evaluation index.

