- (3) The missing values of DCR and primary safety evaluation indicators (proportion of CTCAE grade 3 toxicities, proportion of CTCAE grade 4 and 5 toxicities) at 3 months after the end of treatment can be estimated using worst-case scenarios.
- (4) The missing values of qualitative secondary effectiveness evaluation indicators ORR, DCR and long-term follow-up effectiveness evaluation indicators can be estimated using worst-case scenarios;
- (5) The missing values of quantitative secondary efficacy evaluation indicators DOR, tumor markers, product ease assessment and long-term follow-up effectiveness evaluation indicators were not estimated.
- (6) Erroneous, unreasonable data (out-of-range data and data that contradicts other data or indicators of the study protocol) can be treated as missing values;
- (7) Worst-case estimates are used for missing values for all minor safety indicators;

- (8) The sensitivity analysis of the main effectiveness evaluation indicators and main safety evaluation indicators after treatment was carried out in the whole analysis center.
- (9) The sensitivity analysis of all secondary effectiveness evaluation indicators after treatment was carried out in the whole analysis center.
- (10) For all secondary safety evaluation indicators after treatment, sensitivity analysis was carried out in the security dataset.

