4.3 Effectiveness indicators are missing

When analyzing the main effectiveness evaluation indicators based on PPS, it is not necessary to consider filling them.

In the sensitivity analysis of the main effectiveness evaluation indicators based on FAS, the missing values of the main effectiveness evaluation indicators were not filled.

The missing values of qualitative secondary effectiveness evaluation indicators ORR and DCR were filled by the method of worst observational data carryover (WOCF).

The missing value of the quantitative secondary effectiveness evaluation index DOR was not filled.

Other secondary effectiveness evaluation indicators, such as tumor markers, tumor-specific symptoms, and product ease of use, were not filled.

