5.4 Effectiveness evaluation indicators

5.4.1 Key Effectiveness Indicators

The primary effectiveness evaluation was based on the Full Analysis Set (FAS) and the Protocol-Consistent Set (PPS).

The number and percentage of cases that achieved tumor disease control at 3 months during the follow-up period were calculated, and the 95% confidence interval of tumor disease control rate was calculated by Clopper-

Pearson, and the target value of tumor local control rate was 80%, and if the lower limit of the 95% confidence interval of the test results was greater than 80%, the tumor local control rate was reached. The single-sample chi-square test was used to compare whether there was a statistical difference between the local control rate and the target value.

For the evaluation results of the imaging review team, if the efficacy evaluation results of the two evaluators are consistent, the final evaluation results of the two evaluators will be taken, and if the evaluation results of the two evaluations are inconsistent, the independent evaluation value of the third evaluator will be taken as the final evaluation results.

Based on FAS, the sensitivity analysis of the main effectiveness indicators was carried out, and the missing values of the main effectiveness evaluation indicators were filled by the method of Worst Observational Data Carryover (WOCF).

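### Stopping during radiotherapy counts as not controlled unless coded as loss to follow-up, and the plan does not settle how the exempted patient is scored, so one reason code can change the FAS result

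*Protocol*

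**What the plan says.** **The early-stop rule.** The Protocol summary, under primary effectiveness, states: "Participants who discontinued the trial for any reason (except loss to follow-up) before the end of radiation therapy were considered to have not controlled". The note in Protocol 3.1.4.1 repeats it, with progression as one of the assigned outcomes: "aborted the trial for any reason (except loss to follow-up) before the end of the last radiation therapy were considered to have disease progression (PD"). Protocol 3.1.4.2 has matching notes for objective response rate (ORR), where such patients count as non-responders, and for DCR at the earlier visits. All four places exempt loss to follow-up, and none says what value the exempted patient receives.

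**Missing data, Protocol.** Item (3) of section 4.7.2 covers "The missing values of DCR and primary safety evaluation indicators" and says that those "at 3 months after the end of treatment can be estimated using worst-case scenarios". The wording is permissive and makes no exception by reason. Item (4) says the same of ORR and secondary DCR.

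**Missing data, SAP.** For the FAS sensitivity analysis of the primary endpoint, SAP 4.3 says "the missing values of the main effectiveness evaluation indicators were not filled". For the same analysis, SAP 5.4.1 says "the missing values of the main effectiveness evaluation indicators were filled by the method of Worst Observational Data Carryover (WOCF"), and SAP 5.6 also refers to WOCF. For the PPS, SAP 4.3 considers no filling.

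**Sets and denominator.** The FAS needs one device treatment and one post-baseline observation. The PPS needs measurable disease at baseline and at least one post-baseline assessment of the primary endpoint. It is the main efficacy set, and it prevails if the two sets disagree (Protocol 4.9, SAP 3 and 5.6). The DCR formula divides by the total number of subjects without naming a set (Protocol 3.1.4.1, SAP 2.1.1). SAP 2.1.1, 2.1.2 and 5.4.1 do not carry the early-stop rule.

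**The concern.** Radiotherapy lasts 1 to 8 weeks with repeated attendance. A patient lost before the last fraction is, in practice, one who stopped coming. For the endpoint that is the same event as withdrawal: incomplete treatment and no 3-month assessment. Under the rule, a patient who announces that they are stopping is not controlled, while one who stops without notice falls outside the rule and has no stated score.

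The trial is open-label and single-arm, and it has very little room for failures. If silent dropouts leave the denominator while declared dropouts stay in it as failures, the estimated DCR depends on an administrative distinction. Any bias runs towards reaching the target.

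**Working it through.** **1. Inputs.** Target 80%, expected rate 95%, two-sided alpha 0.05, power 80%, 42 evaluable, 10% dropout and 47 enrolled come from the Protocol summary and 4.2. The pass rule, a lower 95% limit above 80%, is in Protocol 4.5. The Clopper-Pearson method is in Protocol 4.7.1 and SAP 5.4.1.

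**2. The plan's own figure.** For a one-sample test of a proportion with the null variance:

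n = [(1.960 × √(0.80 × 0.20) + 0.842 × √(0.95 × 0.05)) / 0.15]² = 41.59, rounded up to 42.

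42 / 0.90 = 46.7, rounded up to 47. Both figures reproduce.

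**3. Room for failures.** The lower Clopper-Pearson limit for x controlled of n is the 2.5% quantile of a Beta(x, n − x + 1) distribution. At every n from 41 to 47 the rule is met with 3 failures and missed with 4. At n = 47, 44/47 gives 82.5% and 43/47 gives 79.6%.

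**4. One patient, two codes.** Assume 47 treated subjects: 43 controlled, 3 with progression and 1 who stops mid-course.

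| How the mid-course stop is handled | Result | Lower limit | 80% target |
|---|---|---|---|
| Withdrawn: not controlled by the rule | 43/47 | 79.6% | missed |
| Lost, FAS unfilled (SAP 4.3) | 43/46 | 82.1% | reached |
| Lost, worst case applied (Protocol 4.7.2(3)) | 43/47 | 79.6% | missed |
| Lost, kept in a denominator of all subjects | 43/47 | 79.6% | missed |

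Only the second row depends on the code. WOCF is not in the table because scheduled tumour assessments after baseline begin 3 days after the last treatment. A mid-course stopper normally has no post-baseline tumour assessment to carry forward, unless an unscheduled scan exists.

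**5. Effect on power.** Suppose every other patient has a true DCR of 95%, and compare the probability of passing when the mid-course stops count as failures with that when they are left out.

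| Mid-course stops | Counted as failures | Left out |
|---|---|---|
| 0 | 79.3% | 79.3% |
| 1 | 59.4% | 80.3% |
| 2 | 33.5% | 81.3% |
| 3 | 10.5% | 82.3% |

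The numbers of stops are assumptions. The documents give only the 10% overall dropout, about 5 of 47.

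**6. The PPS.** A mid-course stopper with no post-baseline tumour assessment is outside the PPS under either code. The code matters there only if the assigned status of not controlled counts as an assessment, or if an unscheduled scan qualifies the patient. The documents do not say which applies.

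**The case against.** The strongest defence reads the passages together. The exemption only takes lost patients out of an automatic-failure rule. It does not call them controlled and does not remove them from the denominator. Their 3-month value is then simply missing and goes to Protocol 4.7.2(3), which can score it as worst case. A reader might infer that the exemption flatly contradicts 4.7.2(3), but the text does not support that. What stands against the defence is that the worst case is optional, that SAP 4.3 does not use it, and that Protocol 4.4 describes dropouts as outside the primary analysis and lists missing key data as an example. If worst case were always applied, the exemption would have no effect and could be deleted freely.

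Three further readings go too far.

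- **That the code matters in every analysis set and under every fill method.** It does not. Three of the four rows in the table of codes give 43/47, and the governing PPS may exclude the patient either way.
- **That the site alone assigns the code.** Protocol 4.4 has the investigator identify dropouts, but Protocol 4.7.2 sends withdrawal and missing data to investigators and biostatisticians, and SAP 5.3.2 sends set membership to a data review meeting before lock. Sole site control would be an inference.
- **That the 10% dropout measures mid-course losses.** It covers the whole short-term follow-up and includes eligibility violations and prohibited treatments.

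The example also sits on the pass boundary by construction. It shows what one patient can do, and does not forecast what will happen.

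**Conclusion.** The exemption is explicit and repeated, and the score of the exempted patient is not settled. In the FAS left unfilled under SAP 4.3, the reason code of one mid-course stop can move the result from missed (43/47, 79.6%) to reached (43/46, 82.1%). This rests on an assumed count of 3 other failures and 1 mid-course stop, and on the lost patient leaving the denominator. It does not show that the governing PPS result would change.

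The clearest inconsistency is within the SAP. Section 4.3 leaves missing FAS values unfilled, section 5.4.1 fills them by WOCF for the same analysis, and WOCF gives no value to a patient with no post-baseline tumour assessment. The plan should be changed before database lock, because the remedy is cheap and removes a possible bias towards success.

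**What to change.** 1. Delete the exemption for loss to follow-up in the Protocol summary, in the note to 3.1.4.1 and in both notes of 3.1.4.2. Every treated subject who leaves before the end of radiotherapy, for any reason, then counts as not controlled, and as a non-responder for ORR.
2. Carry the same rule into SAP 2.1.1, 2.1.2 and 5.4.1.
3. State that these subjects stay in the FAS denominator and count as failures there, and state whether they count in the PPS. Without this, deleting the words may leave the governing result unchanged.
4. Align SAP 4.3, 5.4.1 and 5.6 with Protocol 4.7.2(3) by scoring any missing 3-month DCR in the FAS as not controlled. This also covers patients lost after radiotherapy and those for whom WOCF has nothing to carry forward.

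The cost is a few words in the Protocol and a few sentences in the SAP, with no new data. DCR and ORR may be slightly lower, and if mid-course stops occur, the chance of reaching the target in the FAS falls as the power table shows.
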